The aim of this postmarket study is to compare the safety and effectiveness of the Altis Single Incision Sling (SIS) to an FDA cleared transobturator and/or retropubic mesh sling through 36 months. The primary safety and effectiveness objectives are as follows:

Primary Safety Objective

To demonstrate that the rate of device and/or procedure related serious adverse events associated with use of Altis SIS is non-inferior compared to the rate associated with use of transobturator and/or retropubic slings at 36 months.

Primary Effectiveness Objective

To demonstrate that the rate of effectiveness associated with use of Altis SIS is non-inferior to the rate associated with use of transobturator or retropubic mesh slings for the treatment of stress urinary incontinence at 6 months.

This study is a prospective, post-market, multi-center, cohort assessment comparing Altis SIS (n=178) and transobturator and/or retropubic slings (n=178) in the treatment of stress urinary incontinence, at up to 40 U.S. and International sites. Subjects will be followed for a total of 36 months with scheduled visits at 6 months, 12 months, 18 months, 24 months, and 36 months.

The study population will consist of adult female subjects with stress urinary incontinence who are clinically indicated for surgical intervention with a mesh sling. All study candidates who provide written informed consent and meet all of the inclusion criteria and none of the exclusion criteria will be included in the study.

Endpoints

Primary Safety Endpoint

- Observed device and/or procedure-related serious adverse events through 36-months.

Primary Effectiveness Endpoint

- Observed effectiveness, defined as a reduction from baseline in 24 hour pad weight of at least 50% at 6 months.

Secondary Safety Endpoints

- Observed rates of device and/or procedure-related adverse events defined as organ perforation, bleeding, mesh exposure in the vagina, mesh erosion into the bladder, pelvic pain, infection, de novo dyspareunia, urinary retention, recurrent incontinence, other urinary problems and neuromuscular problems at 6 months, 12 months, 18 months, 24 months, and 36 months post index procedure.
- All observed adverse events at 6 months, 12 months, 18 months, 24 months, and 36 months.

- Observed revision/re-surgery at 6 months, 12 months, 18 months, 24 months, and 36 months.

Secondary Effectiveness Endpoints

- Observed effectiveness defined as a reduction from baseline in 24 hour pad weight of at least 50% at 12 months, 18 months, 24 months, and 36 months.
- Observed effectiveness for subjects considered dry (pad weight \leq 4.0 grams) at 6, 12, 18, 24, and 36 months.
- Quality of Life at 6 months, 12 months, 18 months, 24 months, and 36 months as measured through:
 - Patient Global Impression of Improvement (PGI-I)
 - Urogenital Distress Inventory (UDI-6)
 - Incontinence Impact Questionnaire-Short Form (IIQ-7)
 - Surgical Satisfaction Questionnaire (SSQ-8)
 - Visual Analog Scale for Pain (VAS Pain)

Inclusion Criteria for Subject Selection

To be included in the study, subjects must meet all of the following inclusion criteria:

1. The subject is female and at least 18 years of age.
2. The subject is able and willing to complete all procedures and follow-up visits indicated in this protocol.
3. The subject has confirmed stress urinary incontinence (SUI) through cough stress test or urodynamics.
4. The subject has failed two non-invasive incontinence therapies (such as Kegel exercise, behavior modification, pad use, biofeedback, etc.) for $>$ 6 months.

Exclusion Criteria for Subject Selection

To be included in this clinical study subjects must not meet any of the following exclusion criteria:

1. The subject has an active urogenital infection or active skin infection in region of surgery.
2. The subject has confirmed Pelvic Organ Prolapse (POP) of Stage 2 or higher as determined by POP-Q prolapse grading.
3. The subject is having a concomitant pelvic floor procedure.
4. The subject has incontinence due to neurogenic causes (e.g. multiple sclerosis, spinal cord/brain injury, cerebrovascular accident, detrusor–external sphincter dyssynergia, Parkinson’s disease, or similar conditions).
5. The subject had a prior surgical SUI treatment.
6. The subject has undergone radiation or brachy therapy to treat pelvic cancer.
7. The subject has urge predominant incontinence by MESA assessment.
8. The subject has an atonic bladder or post void residual (PVR) above 100 cc on \geq 2 occasions.

9. The subject is pregnant and/or is planning to get pregnant in the future.
10. The subject has a contraindication to the surgical procedure or the product IFU.
11. The subject is enrolled in a concurrent clinical trial of any treatment (drug or device) that could affect continence function, without the sponsors' approval.

LIST OF ABBREVIATIONS

ABBREVIATION	DEFINITION

1.2 Investigators

A list of all investigators participating in the study will be maintained in the trial master file at Coloplast.

1.3 Other Representatives

Study management activities including but not limited to database development may be outsourced to appropriate vendors.

2 Study Justification

Urinary incontinence (UI) is defined as the complaint of any involuntary loss of urine.¹ It is a common and distressing medical disorder which is associated with significant decrements in function and quality of life. (QoL). Age, BMI, race, medical comorbidity, current major depression, a history of hysterectomy, parity, and having only had cesarean deliveries are each independent factors significantly associated with the likelihood of having UI.²

Types of urinary incontinence include stress, urge, and mixed incontinence.^{1,3} Stress Incontinence (SUI) is the complaint of involuntary leakage on effort or exertion, or on sneezing or coughing. Urge Incontinence is the complaint of involuntary leakage accompanied by or immediately preceded by urgency. Mixed Incontinence is the complaint of involuntary leakage associated with urgency and also with effort, exertion, sneezing and coughing.¹

Urinary incontinence affects up to 50% of all women and among these 50% to 80% are identified as having SUI. An estimated 4% to 10% of women in the United States undergo surgery intended to restore continence, and this rate has increased steadily during the past 20 years⁴. Additionally, it is commonly assumed by healthcare professionals that UI is an underreported condition, so the actual incidence rate may be much higher.⁵

Surgical treatment of SUI is the most common and the most effective. Surgical procedures performed for SUI increased from 18,820 to 32,480 from 1992 to 2001.⁶ By 2001, more than half of the surgical procedures (17,680) were being done with a pubovaginal sling. The most common pubovaginal sling operations performed in the United States are the Tension-Free Vaginal Tape procedure (TVT)^{7,8} and the transobturator technique (TOT).⁸ In most respects, the TVT and TOT procedures are similar. Both place a hammock like mesh that passes underneath the urethra to provide support and exit through incisions in the abdomen. Tensioning is achieved by pulling the tape through the incisions and suturing the exit wounds. Minimally invasive or single incision slings or "mini-slings" are a recent development to address complications with the traditional slings. Mini-slings are placed through a single incision in the vaginal wall and anchored inside the body. This anchoring inside the body eliminates the exit wounds required for traditional slings. Mini-slings potentially reduce the risk of blind needle passage through the groin or abdomen and may be implanted in an office setting with local anesthesia. All of these factors potentially reduce complications, recovery time, and pain compared to traditional slings.

The Altis Single Incision Sling (SIS) System was developed by Coloplast as a minimally invasive "mini-sling." The Altis SIS System comprises a length of the same material used for the Aris™ Trans-Obturator and Supris™ Retropubic Slings. However, Altis is secured in the obturator foramen and has an integrated tensioning system that eliminates the need for additional skin exits. Effectiveness and safety outcomes of the Altis SIS Sling System were demonstrated in an Investigational Device Study conducted at 17 clinical sites in the United States and Canada. The Altis Sling System received FDA clearance on November 5, 2012, based on Coloplast's submission of IDE study data on 113 study subjects implanted with the Altis SIS.

Manufacturers of single-incision slings have been ordered to conduct post-market studies. These orders were issued on March 13, 2013 for the Altis SIS Sling System under Section 522 of the Federal Food, Drug, and Cosmetic Act. The reason for these orders is "that device failure would be reasonably likely to cause mesh erosion (i.e. organ perforation), severe pain, and fistula formation, which would meet the definition of "serious adverse health consequences" at 21 C.F.R. § 822.3(j)" and because the device is intended to be implanted in the body for more than one year.

3 Study Purpose and Design

3.1 Primary Objectives

The aim of this postmarket study is to compare the safety and effectiveness of Altis SIS to FDA cleared transobturator and/or retropubic slings in the treatment of stress urinary incontinence through 36 months. The primary safety and effectiveness objectives of this study are:

- To demonstrate that the rate of device and/or procedure related serious adverse events associated with use of Altis SIS is non-inferior compared to the rate associated with use of transobturator and/or retropubic slings at 36 months.
- To demonstrate that the rate of effectiveness associated with use of Altis SIS is non-inferior to the rate associated with use of transobturator or retropubic mesh slings for the treatment of stress urinary incontinence at 6 months.

3.2 Secondary Objectives

The secondary objectives of this study are:

- To demonstrate that the rate of device and/or procedure related adverse events defined as organ perforation, bleeding, mesh exposure in the vagina, mesh erosion into the bladder, pelvic pain, infection, de novo dyspareunia, urinary retention, recurrent incontinence, other urinary problems and neuromuscular problems associated with use of Altis SIS is non-inferior compared to the rate associated with use of transobturator and/or retropubic slings at 36 months.
- To demonstrate that the rate of revision/resurgery associated with use of Altis SIS is non-inferior compared to the rate associated with use of transobturator and/or retropubic slings at 36 months
- To provide a descriptive comparison at all time points (6 months, 12 months, 18 months, 24 months, and 36 months) between study groups of the rates associated with the following adverse events: organ perforation, bleeding, mesh exposure in the vagina, mesh erosion into the bladder, pelvic pain, infection, de novo dyspareunia, urinary retention, recurrent incontinence, other urinary problems and neuromuscular problems.
- To assess the effectiveness observed in both study groups at 6 months, 12 months, 18 months, 24 months, and 36 months.
- To assess Quality of Life in both study groups at 6 months, 12 months, 18 months, 24 months, and 36 months.
- To assess the rates, severity, and relatedness of all observed adverse events (including mesh exposure and erosion) associated with both study groups at 6 months, 12 months, 18 months, 24 months, and 36 months.

3.2.1 General

This study is a prospective, post-market, multi-center, cohort assessment comparing Altis SIS (Study Subjects) and transobturator and/or retropubic slings (Control Subjects) in the treatment of stress urinary incontinence. Subjects will be followed for 36 months, with scheduled follow-up visits at 6 months, 12 months, 18 months, 24 months, and 36 months.

[figure not shown]
The study will be analyzed under the intent-to-treat principle. A propensity score analysis will be used to address potential sources of bias due to the cohort design. Additional mechanisms to control potential sources of bias include: rigorous well-defined inclusion/exclusion criteria, utilization of screening and enrollment log, and consecutive enrollment of eligible subjects.

Treatment Group Subjects	Control Group Subjects
Altis Single Incision Sling	Transobturator or Retropubic Slings
N= 178	N= 178

Patient enrollment will continue until the required sample size is successfully reached. The study may include up to 40 U.S. and international sites. No site may attempt to implant more than 20% of subjects in each respective arm without prior approval from Coloplast Corp.

3.2.2 Site and Investigator Selection

Investigators experienced in the use of the study products for treatment of stress urinary incontinence will be recruited to participate in the study.

Figure 1: Overall Study Design Flow-Chart

3.3 Endpoints

3.3.1 Primary Safety Endpoints

- Observed device and/or procedure-related serious adverse events through 36-months.

3.3.2 Primary Effectiveness Endpoint

- Observed effectiveness, defined as a reduction from baseline in 24 hour pad weight of at least 50% at 6 months.

3.3.3 Secondary Safety Endpoints

- Observed rates of device and/or procedure-related adverse events defined as organ perforation, bleeding, mesh exposure in the vagina, mesh erosion into the bladder, pelvic pain, infection, de novo dyspareunia, urinary retention, recurrent incontinence, other urinary problems and neuromuscular problems at 6 months, 12 months, 18 months, 24 months, and 36 months post index procedure.
- Observed adverse events within 6 months, 12 months, 18 months, 24 months, and 36 months of the index procedure.
- Observed revision/re-surgery at 6 months, 12 months, 18 months, 24 months, and 36 months.

3.3.4 Secondary Effectiveness Endpoint

- Observed effectiveness, defined as a reduction from baseline in 24 hour pad weight of at least 50% at 12 months, 18 months, 24 months, and 36 months.
- Observed effectiveness for subjects considered dry (pad weight \leq 4.0 grams) at 6, 12, 18, 24, and 36 months.
- Quality of Life at 6 months, 12 months, 18 months, 24 months, and 36 months as measured through:
 - Patient Global Impression of Improvement (PGI-I)
 - Urogenital Distress Inventory (UDI-6)
 - Incontinence Impact Questionnaire-Short Form (IIQ-7)
 - Surgical Satisfaction Questionnaire (SSQ-8)
 - Visual Analog Scale for Pain (VAS Pain)

3.3.5 Risk Factors

In addition to the primary and secondary endpoint analysis, a propensity analysis will be conducted to address potential risk factors of adverse events and procedural success. Risk factors that will be analyzed include but are not limited to:

- Age
- Parity
- BMI
- Smoking Status
- Diabetes
- Hysterectomy status
- History of Multiple Urinary Tract Infections

3.4 Subjects

The study population will consist of adult female subjects with SUI who are clinically indicated for surgical intervention with a mesh sling. All study candidates who meet all of the inclusion criteria and none of the exclusion criteria and provide written informed consent will be included in the study.

3.4.1 Inclusion criteria for subject selection

To be included in the study, subjects must meet all of the following inclusion criteria:

1. The subject is female and at least 18 years of age.
2. The subject is able and willing to complete all procedures and follow-up visits indicated in this protocol.
3. The subject has confirmed stress urinary incontinence (SUI) through cough stress test or urodynamics.
4. The subject has failed two non-invasive incontinence therapies (such as Kegel exercise, behavior modification, pad use, biofeedback, etc.) for > 6 months.

3.4.2 Exclusion criteria for subject selection

To be included in this clinical study subjects must not meet any of the following exclusion criteria:

1. The subject has an active urogenital infection or active skin infection in region of surgery.
2. The subject has confirmed Pelvic Organ Prolapse (POP) of Stage 2 or higher as determined by POP-Q prolapse grading.
3. The subject is having a concomitant pelvic floor procedure.
4. The subject has incontinence due to neurogenic causes (e.g. multiple sclerosis, spinal cord/brain injury, cerebrovascular accident, detrusor–external sphincter dyssynergia, Parkinson's disease, or similar conditions).
5. The subject had a prior surgical SUI treatment.
6. The subject has undergone radiation or brachy therapy to treat pelvic cancer.
7. The subject has urge predominant incontinence with MESA assessment.

8. The subject has an atonic bladder or post void residual (PVR) above 100 cc on \geq 2 occasions.
9. The subject is pregnant and/or is planning to get pregnant in the future.
10. The subject has a contraindication to the surgical procedure or the product IFU.
11. The subject is enrolled in a concurrent clinical trial of any treatment (drug or device) that could affect continence function, without the sponsors' approval.

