5.2 Procedure Visit

The first surgical implant procedure after the subject is enrolled in the study is considered the index procedure. For newly implanted subjects a standard implant procedure is to be used as detailed in the Instructions for Use for Altis SIS or control product, as applicable. Implant procedure information will be collected as well as medication use during and after the procedure. Any deviation from the procedure should be identified on the appropriate procedure form and detailed on a study deviation form.

The subject will complete a VAS Pain questionnaire each day for the 3 days following their index procedure. The subject will be supplied with a postage paid return envelope to send the questionnaires back to the study site upon completion.

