5.5 Randomization Procedure

There are no randomization procedures in this study.

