6.2.1 Aris® Trans-Obturator Sling

Coloplast Aris Trans-Obturator sling is a permanent, synthetic sub-urethral sling. It is indicated for the surgical treatment of all types of stress urinary incontinence (SUI), for female stress urinary incontinence resulting from urethral hypermobility and/or intrinsic sphincter deficiency (ISD). Aris is made from knitted, monofilament polypropylene and has low elasticity. This structure gives Aris resistance to traction, allows tissue colonization and facilitates positioning during surgery.

The Aris sling is provided sterile and is for single-use only. The Aris sling is sterilized by ethylene oxide. Introducer Needles are available and intended to facilitate the placement of the Aris Trans-Obturator Sling.

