12.6.3. Propensity Score Analysis

In addition to the analyses of the primary effectiveness and safety endpoints noted above, a propensity analysis will be conducted to address the effect of potential confounding variables on study conclusions. Risk factors that will be analyzed include, but are not limited to:

- Age
- Parity
- BMI
- Smoking status
- Diabetes
- Hysterectomy status
- History of Multiple Urinary Tract Infections

For this analysis, a logistic regression model will be used to calculate the probability of treatment assignment given the covariates listed above (i.e., the propensity score). The covariates will not be grouped, resulting in one propensity score for each subject. The propensity score will be used in an adjusted regression model for each primary endpoint. A logistic regression model will be used for the primary effectiveness and safety endpoints.

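### The propensity model, the plan's main analytic check on selection, lists no measure of incontinence severity, although baseline pad weight, UDI-6 and IIQ-7 are collected in both arms

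*Protocol*

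**What the plan says.** Protocol 5.5 states: "There are no randomization procedures in this study". The documents give no rule for choosing the sling. Protocol 3.2.1 names the analytic answer: "A propensity score analysis will be used to address potential sources of bias due to the cohort design". It adds well-defined eligibility criteria, a screening and enrollment log, and consecutive enrollment as further controls.

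Protocol 3.3.5 and SAP 12.6.3 list the same seven risk factors: age, parity, BMI, smoking, diabetes, hysterectomy and multiple urinary tract infections. Both lists are introduced as non-exhaustive. Protocol 7.8 and SAP 12.6.3 then describe a logistic model used to "calculate the probability of treatment assignment given the covariates listed above (i.e., the propensity score"). The score enters a logistic regression for each primary endpoint.

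This analysis is additional. Under Protocol 7.4 and SAP 12.6.1, effectiveness is decided by an unadjusted Z-test against a margin of 0.15.

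The baseline visit (Protocol 5.1 and Table 1) includes the 24-hour pad weight test, UDI-6 and IIQ-7. SAP 12.6.1 names baseline pad weight as a candidate imputation variable. SAP 12.10 uses it to define subgroups at 4 g and 1.3 g.

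On suitability for a device, Protocol 3.4 describes women "who are clinically indicated for surgical intervention with a mesh sling". Exclusion 10 in Protocol 3.4.2 reads: "The subject has a contraindication to the surgical procedure or the product IFU".

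**The concern.** When the surgeon and patient choose the sling, severity of incontinence could plausibly influence both the choice and the outcome. A propensity model removes only the imbalance carried by the variables in it. Here the severity measures are recorded, and one of them, baseline pad weight, is the reference value for the primary endpoint of at least a 50% reduction. The SAP considers that variable relevant to imputation and to subgroups, yet does not list it for confounding.

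At stake is what the propensity analysis can be used to say. If it agrees with the unadjusted result, a reader will take that as evidence that selection did not drive the conclusion. For severity, the model as listed cannot give that assurance, except so far as the seven covariates happen to be correlated with it.

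**Working it through.** **The plan's own figures.** Per-arm size by the unpooled normal approximation, one-sided alpha 0.025, power 80%, with (1.960 + 0.842)² = 7.849:

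- Effectiveness (75% in both arms, margin 0.15): 7.849 × (2 × 0.75 × 0.25) / 0.15² = 130.8, so 131. With 20% loss, 131 / 0.8 = 163.75, so 164. Both match Protocol 7.9.2.
- Safety (10% in both arms, margin 0.10): 7.849 × (2 × 0.10 × 0.90) / 0.10² = 141.3, so 142. With 20% loss, 142 / 0.8 = 177.5, so 178. Both match Protocol 7.9.3 (SAP 10.2 states the 142).

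These sizes are not in question. The point is bias, not precision.

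**Where baseline severity appears in the plan.**

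| Place | Baseline severity used? |
|---|---|
| Protocol 5.1 and Table 1 | Collected: pad weight, UDI-6, IIQ-7 |
| SAP 12.6.1, multiple imputation | Pad weight, as a candidate |
| SAP 12.10 (4 g also in Protocol 7.2) | Pad weight, as subgroup cut-offs of 4 g and 1.3 g |
| SAP 12.4, baseline comparison | Not named; list open-ended |
| Protocol 3.3.5 and 7.8, SAP 12.6.3 | Not named; list open-ended, model on the covariates listed |
| Deciding Z-test, SAP 12.6.1 | None |

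**How large could it be?** The documents do not say, so the following is illustration only. Let f be the excess share of severe cases in the control arm over the Altis arm, and d the amount by which their success rate is lower. The observed control rate then falls by f × d.

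Take Altis exactly at the margin among comparable women (75% control, 60% Altis) and 142 evaluable per arm (178 less 20%). The chance of wrongly declaring non-inferiority on the unadjusted test is

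Φ[(0.15 − (p_C − 0.60)) / SE − 1.96], with p_C = 0.75 − f × d and SE = √[(p_C(1 − p_C) + 0.60 × 0.40) / 142].

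| f | d | f × d | p_C | False non-inferiority |
|---|---|---|---|---|
| 0 | 0 | 0 | 0.750 | 2.5% |
| 10% | 10 points | 0.010 | 0.740 | 3.8% |
| 10% | 15 points | 0.015 | 0.735 | 4.6% |
| 20% | 20 points | 0.040 | 0.710 | 10.6% |
| 20% | 30 points | 0.060 | 0.690 | 18.4% |
| 30% | 30 points | 0.090 | 0.660 | 35.0% |

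If the excess lies in the Altis arm, the bias reverses. With true rates of 75% in both arms, power at 142 per arm is Φ(0.15 / 0.0514 − 1.96) = 83%. With f × d = 0.040 taken off the Altis rate (0.71), SE is 0.0526 and power is Φ(0.11 / 0.0526 − 1.96) = 55%.

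Both sets of figures describe the unadjusted test. They show how much selection on severity could matter if it occurred, and so why the check on it should include severity. They do not measure the effect of the fix, which leaves that test as it is.

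**The case against.** The strongest reply is that the plan is not closed to severity. Both covariate lists can be extended. SAP 12.4 compares baseline characteristics, including the history of SUI, and provides for assessing relevant factors when groups differ significantly. The leakage subgroups look at severity directly. Exclusions for prolapse, concomitant procedures, prior SUI surgery, pelvic radiation and urge-predominant incontinence already make the arms more alike. And nothing in the documents shows that heavier leakage lowers the chance of a 50% relative reduction.

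Much of this stands. It rules out saying that the plan cannot address severity, and it leaves direction and size open. It does not amount to a commitment. An open list leaves covariate choice to be made later in an unblinded study. SAP 12.4 waits for a significant difference and names neither the severity measures nor the method. A subgroup above a cut-off does not balance severity within that subgroup.

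A reader might infer more: that the control arm contains women who could never have received Altis. The inference would run from the singular product in exclusion 10, from the procedure section's "Instructions for Use for Altis SIS or control product, as applicable", and from the description of Aris as indicated "for female stress urinary incontinence resulting from urethral hypermobility and/or intrinsic sphincter deficiency (ISD"), when the Altis description mentions neither condition. The documents do not support it. Exclusion 10 is ambiguous and could cover any study product. Protocol 5.2 concerns implant technique, not eligibility. Protocol 6.1 describes the Altis device and is not an indication statement, so its silence proves nothing. No Instructions for Use are included, and no contraindication that differs between slings is shown.

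**Conclusion.** The point holds as a gap in prespecification. The plan's main analytic check on selection lists seven covariates, none of them a measure of incontinence severity, while three such measures are taken before surgery in both arms. As written, the check may leave confounding by severity unadjusted.

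Direction and size are unknown. The illustrative shifts of 0.010 to 0.090 (7% to 60% of the 0.15 margin) rest wholly on assumed shares and deficits. The upper end is an extreme combination with Altis exactly at the margin, and the bias can run against Altis.

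Two stronger conclusions should not be drawn. The documents do not show control women who were never candidates for Altis. Nor do they justify removing such women later from the per-protocol set: that would need a suitability judgment that the data schedule does not record, made in an open-label study, and could itself add bias.

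**What to change.** 1. In Protocol 3.3.5 and 7.8 and in SAP 12.6.3, name baseline 24-hour pad weight, UDI-6 and IIQ-7 as covariates in the propensity model. The SAP change matters most, because the SAP prevails where the two differ. Add MESA scores only if they are in the database: MESA appears as an eligibility screen and not in the data collection schedule.
2. Report the distribution of propensity scores by arm and their overlap. Adding severity covariates balances severity only where the arms overlap, so the report should show where they do not.
3. As a clarification only, state which product's Instructions for Use exclusion 10 refers to.

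The cost is a short text change and a little analysis work on data already collected. The primary Z-test, the margin and the sample size stay as they are.
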